# 6.1.2. Definition of Study Baseline

Unless otherwise specified, for efficacy and health outcome, baseline is defined as the last nonmissing assessment recorded on, or prior to, the date of the first study drug administration at study Day 1.

Baseline for safety analyses is described in the safety section.

Change from baseline will be calculated as the visit value of interest minus the baseline value. If a baseline values or the value at the visit is missing for a particular variable, then the change from baseline is defined as missing.

# 6.1.3. Study Time Intervals

To calculate the length of any time interval or time period in this study, the following formula will be used:

 $Length\ of\ interval\ (days) = End\ Date - Interval\ Start\ Date + 1$ 

To convert any time length from days to weeks, the following formula will be used:

Length of interval (weeks) = Length of interval (days)/7

Only for the purpose of calculating the length of study period time intervals, the words "prior to" in Table PYAB.6.2 should be understood to mean "the day before" while the words "after" should be understood to mean "the day after." For the purpose of determining whether a date/time lies within an interval, these words are intended to convey whether the start or end of the period is inclusive of the specified date.

Table PYAB.6.2. Definition of Study Period Time Intervals

Study Period	Interval Start Definition	Interval End Definition
Screening: All participants who sign informed consent/assent are considered as entering the Screening Period.	Informed consent/assent date	Prior to the start of Treatment and Assessment Period.
Treatment and Assessment Period: All participants who have treatment initiated are considered as entering the Treatment Period.	At the start of study drug administration date/time.	The minimum of treatment period discontinued date, study discontinuation date, or first Post-Treatment Follow-Up visit date.
Post-Treatment Follow-Up: All participants who had a follow-up visit are considered as entering follow-up period.	After the Treatment and Assessment Period ends.	The maximum of the last study visit date or study disposition date.

Estimates of continuous efficacy, safety, and health outcome variables with a single postbaseline timepoint will be made using analysis of covariance (ANCOVA) with baseline value in the model. The LS mean, standard error, and 95% CI, unless otherwise specified, will also be reported. Missing data imputation method for the ANCOVA model is specified in Section 6.3.

Estimates of binary endpoints will be made using logistic regression. The model will include the weight range groups used for dosing, unless otherwise noted. The CIs of any rate estimates will be reported.

The Kaplan-Meier (KM) product limit method will be used for time-to-event analyses. Time for all analyses will be described in units of days.

For all change from baseline analyses, patients who do not have a valid baseline measure will be excluded.

# 6.2. Adjustments for Covariates

Unless otherwise specified, efficacy analyses will adjust for the baseline value of the endpoint and by dosing weight category when modeling estimates.

# 6.3. Handling of Dropouts or Missing Data

The SoA, outlined in the protocol addendum, specifies the allowable windows for assessments. Assessments performed outside these windows will not be excluded from any analysis but may be reported as a protocol deviation (see Section 6.14).

# 6.3.1. Non-Responder Imputation

For analysis of categorical efficacy and pharmacodynamic variables, missing data will be imputed using a non-responder imputation (NRI) method. Participants will be considered non-responders for the NRI analysis if they do not meet the categorical efficacy criteria or have missing clinical efficacy data at a time point of interest.

# 6.3.2. Modified Non-Responder Imputation

For analysis of viral clearance (yes/no), missing data will be imputed using modified nonresponder imputation (mNRI). Specifically, for patients that have missing postbaseline data for RT-PCR testing for SARS-CoV-2 (based on nasopharyngeal swab sampling) then viral clearance status will be imputed as follows:

If a participant has previously achieved viral clearance (i.e., the participant previously had 2 consecutive negative tests), then viral clearance will be imputed as "Yes."

If a participant has not previously achieved viral clearance (i.e., the participant does not have 2 consecutive previous negative tests), then viral clearance will be imputed as "No."

After imputation, data from all participants will be included in the analyses. The application of mNRI to viral clearance helps ensure that the maximum number of randomized participants are represented in the analysis.

# 6.3.3. Mixed-Effects Model Repeated Measures

For continuous variables, the primary analysis will be MMRM with the MAR assumption for handling missing data. This analysis considers both missingness of data and the correlation of the repeated measurements. No imputation methods will be applied to the MMRM analysis.

For all change from baseline analyses, patients who do not have a valid baseline measure will be excluded from the model.

# 6.3.4. Highest Disease States Imputation

For the analyses related to National Institute of Allergy and Infectious Diseases (NIAID)/World Health Organization (WHO) ordinal scales, the following imputation will be considered if applicable.

For participants whose data are missing during any hospitalization period (not yet recovered), a score of 7, which is the highest value for a hospitalization status, will be used for imputation.

For participants whose data are missing after recovery or discharged, a score of 3, the highest value for a recovery or nonhospitalized status, will be used for imputation.

### 6.3.5. Last Observation Carried Forward

Analyses of PHVL on Day 7 will utilize a last observation analysis (LOCF). The LOCF method is performed by carrying forward the last nonmissing assessment. If only the baseline viral load is nonmissing, then the baseline is carried forward.

### 6.3.6. Modified Last Observation Carried Forward

Analyses of symptom data, with the exception of change in symptom score, will utilize a modified last observation analysis (mLOCF). The mLOCF method is performed by carrying forward the last nonmissing postbaseline assessment to the subsequent missing assessments for analysis. For patients who die, all missing collection time points subsequent to the date of death will be imputed to Severe.

After mLOCF imputation, data from participants with nonmissing baseline and at least 1 postbaseline observation will be included in the analyses. The mLOCF imputation helps ensure that the maximum number of randomized participants who were assessed postbaseline will be included in the analyses and unfavorable terminal events are represented.

### 6.4. Multicenter Studies

Differences between study centers will not be a feature of the statistical analyses for this study. Baseline variables and demographics may be described by site.

Individual center results may be presented, where appropriate, when the centers have sufficient numbers of participants to make such analysis potentially valuable. The possibility of qualitative or quantitative treatment-by-center interaction may be explored.

# 6.5. Multiple Comparisons/Multiplicity

Treatment Arm 23

Control for multiplicity is not applicable as this is a single-arm cohort.

# 6.6. Participant Disposition

The treatment period disposition and study disposition will be summarized for the safety population. Summaries will also include reason for discontinuation from the study.

All participants who are treated and discontinued from study treatment or from the study will be listed, and the timing of discontinuing the study (from treatment date) will be reported. If known, a reason for their discontinuation will be given.

In addition, a graphical summary (i.e., KM plot) of time from treatment to early permanent discontinuation of study or study treatment due to AEs may be generated if there are a substantial number of such events.

Table PYAB.6.4. Tables and Figures Related to Disposition

Analysis	Details
Patient Disposition	Number and percentage of participants by reason for
	study discontinuation and
	study treatment period discontinuation
Listing of study and study treatment	
disposition	
Listing of participants discontinuing	Variables included the reason for study discontinuation, the text
due to a decision-related reason (loss	collected in the specify field associated with the reasons for
to follow-up, patient decision, or	discontinuation, and the dates of discontinuation
investigator decision)	
	The text in the specified field should provide information to support that
	the reason is unrelated to efficacy or safety
Time to early discontinuation of study	Presented as a figure (if necessary)
treatment due to adverse events (AEs)	

# 6.8. Treatment Compliance

As all study drug doses will be administered at the study site, treatment compliance will not be reported.

# 6.9. Prior Medication and Concomitant Therapy

Medications will be classified into anatomical therapeutic chemical (ATC) drug classes using the latest version of the WHO drug dictionary. Medication start and stop dates will be compared to the date of the first dose of treatment to allow medications to be classified as concomitant.

Prior medications are those medications that start and stop prior to the date of the first dose of study treatment. Concomitant medications are those medications that start before, on, or after the first day of study treatment and continue into the treatment period.

For all summary tables of concomitant medications, Preferred Terms of concomitant medication will be sorted by descending frequency in the LY total arm.

Table PYAB.6.6. Summary Tables Related to Concomitant Medications

Analysis	Details
Prior medications	Number and percentage of participants using Preferred Terms of prior medication Ordered by decreasing frequency No inferential statistics
Concomitant medications	Number and percentage of participants using Preferred Terms of concomitant medication Ordered by decreasing frequency No inferential statistics

# 6.10. Efficacy Analyses

The analysis of the viral load lab results will utilize the following conventions:

For qualitative endpoints in the trial (viral clearance yes/no, time to viral clearance) the lab determination of "positive"/ "negative" will be used. SARS-CoV-2 clearance (yes/no) is defined as 2 consecutive negative tests for the SARS-CoV-2 virus. The date of viral clearance is defined as the earliest date of the 2 consecutive negative tests.

For quantitative endpoints in the trial (change from baseline, area under the response viral load curve [AUC]), the viral load will be derived based on cycle threshold (Ct) values with the following considerations:

Two Ct values will be provided on 2 different genes: N1 and N2. N1 will be used as the primary measure; N2 will only be used when the Ct value for N1 is not available.
Ct values range between 0 and 45.
Negative CoV-2 tests will be associated with a Ct value of 45.
The (log base 10) viral load will be calculated from the Ct value (45-Ct)/log 10, or (45-Ct)/3.321928.

□ A normalization step will also be applied. The viral load Ct value described in the previous steps will be subtracted by (RP Ct – 26.17), where RP Ct is a measure for the amount of material in the sample and 26.17 is a historical average value of RP Ct for this assay, used here to center the RP Ct values.

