COVID-19 Symptoms	X	X	X	X	X	X	X	X	X	X	X				Day 1: assess prior to dosing The presence of absence of symptoms are collected from the participants or their parents/legal guardian.
Laboratory Tests and Sample Collections															
Hematology		X		X				X		X	X				Day 1: before treatment administration All other days: sample may occur at any time during the day Lilly-designated central laboratory

	Period I Screening	Period II Treatment Period											Period III Post- Treatment Follow-Up		
Study Day from Treatment Assignment		1	2, 3, 4	5	6	7	8, 9, 10	11	22	29	ED	Follow-up if hospital inpatient on Day 29	60	85	
Visit interval tolerance (days)		—	—	±1	—	+1	—	±2	±2	±3	±2	Every 7 days until discharge or Day 60	±4	±4	
Visit Detail		O	T,I	O,H	T,I	O,H	T,I	O,H	T,I	O,H	O,H		O,H	T,I	O = Outpatient clinic, H = Home Visit, T = Telephone, I = IT-Assisted Virtual Visit
Clinical Chemistry		X		X				X		X	X				Day 1: before treatment administration All other days: sample may occur at any time during the day Lilly-designated central laboratory
Documentation of positive SARS-CoV-2 viral infection	X														Sample for first positive test must be collected within 3 days prior to start of treatment administration. Local laboratory and/or Point-of- Care testing.
PD swab		X		X		X		X		X	X				Swab is taken from both nostrils. Day 1: swab before treatment administration. Methods include nasopharyngeal (preferred) or mid-turbinate. The same method of sample collection must be used per participant for the duration of the study. Switching methods is not allowed. Lilly-designated central laboratory

	Period I Screening	Period II Treatment Period											Period III Post- Treatment Follow-Up		
Study Day from Treatment Assignment		1	2, 3, 4	5	6	7	8, 9, 10	11	22	29	ED	Follow-up if hospital inpatient on Day 29	60	85	
Visit interval tolerance (days)		—	—	±1	—	+1	—	±2	±2	±3	±2	Every 7 days until discharge or Day 60	±4	±4	
Visit Detail		O	T,I	O,H	T,I	O,H	T,I	O,H	T,I	O,H	O,H		O,H	T,I	O = Outpatient clinic, H = Home Visit, T = Telephone, I = IT-Assisted Virtual Visit
Serum or Urine pregnancy (local)	X														Pregnancy tests prior to the first dose of investigational product for females if 
 aged ≥10 years <10 years at investigator’s discretion menarche is reached or there is reason to believe that the patient is sexually active. Local laboratory

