2.4.1. Section 4.1.1. Design Outline

Careful consideration was given to collect the necessary information to address the key scientific objectives of this pediatric study while also minimizing invasive procedures and overall patient burden, including through the use of comfort measures (e.g., EMLA cream) during blood draws.

This table describes the visit types for this study.

Study Day	Visit Type
1	Outpatient clinic visit
2, 3, 4, 6, 8, 9, 10, 22, and 85 (follow-up visit)	Telephone / IT-assisted virtual visits
5, 7, 11, 29, ED and 60 (follow-up visit)	May be conducted as outpatient clinic or home visits

Abbreviation: ED = early discontinuation.

Refer to the SoA (Addendum Section [2.2.1](#)) for the list of procedures in this study.

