# 6.11. Bioanalytical and Pharmacokinetic/Pharmacodynamic Methods

Pharmacokinetic and PD analyses are the responsibility of the Eli Lilly and Company PK/PD group.

Bebtelovimab concentration data will be analyzed using a population PK approach via nonlinear mixed-effects modeling with the NONMEM software. In addition, the effects of participant factors, such as weight and age on PK parameters may be evaluated. If antidrug antibody is detected from immunogenicity testing, its impact on bebtelovimab PK may also be evaluated.

A limited number of pre-identified individuals may gain access to interim data prior to the primary lock, in order to initiate the population PK/PD model development processes.

Pharmacodynamic endpoints will be summarized using descriptive methodology. The SARS-CoV-2 viral dynamics will include evaluation of

change from baseline in SARS-CoV-2 viral load (Days 5, 7, and 11) AUC, and time to SARS-CoV-2 clearance.

Additional PK/PD concentration-response analysis may be performed PK/PD analyses on adolescents in the study will be treated as secondary to support the pediatric analyses.

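### Viral clearance needs two consecutive negative swabs, so on the planned swab days no clearance can be dated after the Day 11 visit and a first negative on Day 29 counts as not cleared

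*SAP*

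**What the plan says.** **Definition.** SAP 6.10 states: "SARS-CoV-2 clearance (yes/no) is defined as 2 consecutive negative tests for the SARS-CoV-2 virus". It goes on: "The date of viral clearance is defined as the earliest date of the 2 consecutive negative tests".

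**Use.** SAP 6.10 names clearance (yes/no) and time to clearance as the qualitative viral endpoints. SAP 6.11 lists among the viral dynamics to be evaluated "AUC, and time to SARS-CoV-2 clearance", summarised descriptively.

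**Swab days.** In the Schedule of Activities for Arm 23 (Protocol 2.2.1) the column heads run "Study Day from Treatment Assignment 1 2, 3, 4 5 6 7 8, 9, 10 11 22 29 ED", followed by the inpatient follow-up, Day 60 and Day 85 columns. The swab row reads "PD swab X X X X X X Swab is taken from both nostrils". The six marks stand under Days 1, 5, 7, 11, 29 and ED. None stands under Day 22, inpatient follow-up, Day 60 or Day 85.

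**Day 22.** Protocol 2.4.1 classes it with the remote contacts: "2, 3, 4, 6, 8, 9, 10, 22, and 85 (follow-up visit) Telephone / IT-assisted virtual visits".

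**Missing tests.** SAP 6.3.2 imputes clearance status when a swab is missing. The negative branch begins "If a participant has not previously achieved viral clearance (i.e., the participant does not have 2 consecutive previous negative tests" and sets the status to No.

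**The concern.** A rule that needs a confirming test can register a new event only at a visit that has another swab after it. Day 29 has none. The Day 29 swab can confirm a negative first seen at the Day 11 visit, but it can never start a clearance of its own.

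A child who becomes negative between the two visits is then indistinguishable, under the rule, from a child still positive on Day 29. Any reported clearance proportion would mean first of two negatives by the Day 11 visit, whatever its label. A time-to-clearance curve could show no events after that visit, and a reader could take the flat stretch for viral persistence when it comes from the swab schedule.

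**Working it through.** The plan states no rate, power or sample size for clearance, so there is no figure to reproduce. The check applies the rule to every result sequence the schedule allows.

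**Inputs**
- Swab days 1, 5, 7, 11, 29, or an ED swab in place of the later ones (Protocol 2.2.1). ED applies to discontinuation before the last treatment-period visit, so it does not follow Day 29.
- Rule: two consecutive negatives, dated at the first (SAP 6.10).
- Visit windows: Day 11 ±2 days, Day 29 ±3 days (Protocol 2.2.1).
- About 50 participants aged 0 to 12 years (SAP 5.3).
- Share of children positive on Day 11 and negative on Day 29: not in the documents.

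**Step 1: all patterns.** Five swabs give 2^5 = 32 positive/negative sequences. The rule dates them as follows:

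| Clearance date | Sequences |
|---|---|
| Day 1 | 8 |
| Day 5 | 4 |
| Day 7 | 4 |
| Day 11 | 3 |
| None | 13 |
| Total | 32 |

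No sequence is dated Day 29. Repeating this with any subset of scheduled swabs missing, or with an ED swab on any day from 2 to 28 replacing the later swabs, again gives only Days 1, 5, 7 and 11.

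**Step 2: children who turn negative and stay negative** (results on Days 1, 5, 7, 11, 29)

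| First negative | Results | Date under SAP 6.10 |
|---|---|---|
| Day 5 | + − − − − | Day 5 |
| Day 7 | + + − − − | Day 7 |
| Day 11 | + + + − − | Day 11 |
| Day 29 | + + + + − | none |
| Never | + + + + + | none |

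The last two rows get the same result.

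**Step 3: missing Day 29 swab.** For + + + − followed by a missing swab, there are not two earlier consecutive negatives, so SAP 6.3.2 gives No.

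**Step 4: length of the gap.** Nominal: 29 − 11 = 18 days. Shortest within windows: (29 − 3) − (11 + 2) = 26 − 13 = 13 days. Longest: (29 + 3) − (11 − 2) = 32 − 9 = 23 days.

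**Step 5: how many children.** Number affected = 50 × share with the pattern + + + + −. The shares are assumptions only.

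| Assumed share | Children of 50 |
|---|---|
| 5% | 2.5 |
| 10% | 5 |
| 20% | 10 |
| 30% | 15 |
| 50% | 25 |

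**The case against.** **Low weight.** Clearance is not in the protocol's endpoint table (Protocol 2.3) or in its list of viral dynamics (Protocol 2.10.4.4). The SAP adds it as a descriptive item in a single-arm study whose primary endpoint is pharmacokinetic. SAP 6.1 makes exploratory analyses conditional on the team judging them warranted. SAP 6.16.1.1, on viral load, specifies no clearance analysis. This stands, and it limits how much the point matters. It does not make the rule work.

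**Requiring confirmation is deliberate.** Any confirmed-event definition loses first events at the last visit. This also stands. But the plan does not say that the endpoint stops at the Day 11 visit, and it has no category for a lone negative at the end.

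**Stronger readings the documents do not support.**
- A reader might infer that no child can have a clearance date after calendar Day 11. The limit is the Day 11 visit, whose window runs to Day 13, and SAP 6.3 keeps out-of-window assessments. An unscheduled swab could also confirm a Day 29 negative, though neither document plans one.
- A reader might infer that late clearers are counted as failures throughout. That is exact for the yes/no endpoint. In a Kaplan-Meier analysis, the general method in SAP 6.1.4, they would presumably be censored. The SAP does not say, although it does set censoring rules for symptom resolution (6.16.1.3) and hospitalization (6.16.2.1).
- A reader might infer that a Day 29 cleared proportion is planned and will be wrong, or that the whole time-to-clearance analysis is invalid. No such proportion is specified, and children confirmed by the Day 11 visit are dated as defined.
- A reader might size the problem from the 0.158 daily decrease in SAP 6.16.2.6. There it only adjusts plotted loads for days since symptom onset. It is not offered as a post-dose rate, and clearance rests on the laboratory's positive/negative call. A percentage built on it would also need a baseline distribution that the documents do not give.

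**Conclusion.** The point holds as a structural one. On scheduled swabs, with or without missing visits or an ED swab, clearance cannot be dated later than the Day 11 visit. A child first negative on Day 29 is classed as not cleared for the yes/no endpoint and can contribute no event to time to clearance, which has no stated censoring rule. A first negative on Day 11 without a Day 29 swab is also set to No.

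Both losses act in one direction: they can only overstate persistence. Their size cannot be determined from the documents; the 2.5 to 25 children above follow from an assumed range. The conclusion rests on the scheduled swabs alone, and the main protocol was not available. No pharmacokinetic or safety conclusion is shown to depend on this endpoint. The change is worth making before data are seen because SAP 6.11 commits to the output and the cohort is open-label.

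**What to change.** In SAP 6.10, 6.11 and 6.3.2:

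1. Define the confirmed endpoint as clearance by the Day 11 visit: the first of two consecutive negatives, with the Day 29 or later ED swab serving only as confirmation.
2. End the time-to-clearance summary at the Day 11 visit and censor there the children without confirmed clearance. State this censoring rule.
3. Report separately the proportion of swabs negative at Day 29 (or at ED).
4. List a lone negative at a child's last available swab as unconfirmed rather than No. This covers a first negative on Day 29, a first negative at ED, and a first negative on Day 11 with no later swab.

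**Cost.** SAP wording and a small programming change; no new swab or visit. The drawback is that later clearance is then described only by single, unconfirmed negatives, which the label makes plain.

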2.7.1. Section 5.1. Inclusion Criteria

Participants are eligible to be included in this addendum only if all of the following criteria apply:

1. This criterion is not applicable to participants in this addendum
2. This criterion is not applicable to participants in this addendum
3. This criterion is not applicable to participants in this addendum
4. Must have first positive result sample of current SARS-CoV-2 viral infection ≤ 3 days prior to start of the administration
5. Are males or females
Reproductive and Contraceptive requirements are provided in the main PYAB protocol, Section 10.4, Appendix 4. Contraceptive use by males or females should be consistent with local regulations for those participating in clinical studies.
6. The participant and/or legally authorized representative understand and agree to comply with planned study procedures
7. The participant and/or legally authorized representative agree to the collection of nasopharyngeal swabs and venous blood
8. The participant or legally authorized representative give signed informed consent and/or assent as described in the main PYAB protocol, Section 10.1.3 which includes compliance with the requirements and restrictions listed in the informed consent form (ICF) and in this protocol.
27. This criterion is not applicable for participants in this addendum
28. This criterion is not applicable for participants in this addendum
36. Are 0 (≥ 38 weeks gestational age and ≥ 3.3 kg) to <12 years of age at the time of screening, or are 12 to 17 and weighing <40 kg.
37. Have mild to moderate COVID-19 disease, including one or more of the following symptoms, within the last 7 days (FDA February 2021; CDC January 2022; CDC March 2022.)
 - shortness of breath or difficulty breathing
 - fever
 - sore throat
 - nausea
 - diarrhea
 - nasal congestion or runny nose
 - chills
 - malaise
 - vomiting
 - cough

- tiredness
- headache
- new loss of taste
- muscle or body aches and pain
- new loss of smell, or
- poor appetite or poor feeding (especially in babies under 1 year old).

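### Viral clearance can be recorded from a pre-dose swab, and children negative on the central Day 1 swab are not separated from the rest

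*SAP*

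**What the plan says.** **Entry.** Inclusion criterion 4 (Protocol 2.7.1) reads: "Must have first positive result sample of current SARS-CoV-2 viral infection ≤ 3 days prior to start of the administration". The Schedule of Activities (Protocol 2.2.1) repeats this, "Sample for first positive test must be collected within 3 days prior to start of treatment administration", and allows local or point-of-care testing.

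**Baseline swab.** The pharmacodynamic swab is a separate sample sent to the central laboratory: "Day 1: swab before treatment administration". Later swabs are on Days 5, 7, 11 and 29 and at early discontinuation. No inclusion or exclusion criterion depends on the Day 1 result.

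**Clearance.** SAP 6.10: "SARS-CoV-2 clearance (yes/no) is defined as 2 consecutive negative tests for the SARS-CoV-2 virus". The date is the earlier of the two: "The date of viral clearance is defined as the earliest date of the 2 consecutive negative tests". SAP 6.3.2 imputes later missing results as cleared once two consecutive negatives have been seen. SAP 6.11 lists "time to SARS-CoV-2 clearance" among the viral dynamics to be summarized.

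**Value of a negative.** SAP 6.10: "Negative CoV-2 tests will be associated with a Ct value of 45". A normalization for the amount of material on the swab (RP Ct) follows.

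**Who is analyzed.** The efficacy population (SAP 6.1.1) needs treatment and one postbaseline efficacy measurement. Baseline (SAP 6.1.2) is the last nonmissing value on or before the dosing date. SAP 6.3.3 says that "patients who do not have a valid baseline measure will be excluded from the model", and SAP 6.1.4 has the same rule. Neither section says what makes a baseline valid.

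**The concern.** An outcome meant to describe what happens after treatment can be met partly on a sample taken before treatment. A child who is negative before dosing needs only one post-dose negative to count as cleared, while a child who is positive needs two.

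The baseline-negative child also has no measurable virus to lose. Counting such children pushes the clearance proportion up and pulls the mean fall in viral load toward zero. The amount depends on how local tests and test timing relate to the central assay, not on the drug. The cohort is uncontrolled, so no comparator carries the same contamination, and the viral results may also feed the optional PK/PD analyses in SAP 6.11.

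**Working it through.** The documents give no power, precision or event figure for viral load or clearance, so there is no planned figure to reproduce. The conversion constant is right: log2(10) = 3.321928, as SAP 6.10 states.

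**1. Apply the rules to one child: negative on Day 1 pre-dose, negative on Day 5.**
- Clearance: two consecutive negatives, so yes.
- Date: the earlier test, so Day 1.
- Time: SAP 6.11 gives no formula for time to clearance. The general interval formula in SAP 6.1.3 gives Day 1 − Day 1 + 1 = 1 day. With post-dose swabs only, the earliest possible date is the Day 5 visit.
- Later missing swabs: imputed as cleared under SAP 6.3.2.

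**2. Is this child in the change from baseline?** A negative is assigned Ct 45, so the baseline is not missing. SAP 6.16.2.6 treats an observed viral load of zero as data. Inclusion is therefore the likely reading, but the undefined term 'valid' leaves it open.

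The baseline load is (45 − 45)/3.321928 = 0 before normalization. After normalization it is (RP Ct − 26.17)/3.321928. With assumed RP Ct values of 23 and 29, this gives −3.17/3.321928 = −0.95 and 2.83/3.321928 = +0.85. If the child stays negative, any change reflects only swab material.

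**3. Is this child in the viral AUC?** SAP 6.16.1.1 uses only values above the lower limit of quantification (LLOQ) and calculates no AUC when the Day 1 value is missing. It does not say whether a below-LLOQ Day 1 value counts as missing. The child may have no AUC at all.

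**4. Illustrate the size.** Assumed inputs, none of them in the documents: share negative at baseline f = 5%, 10%, 20%; true clearance among baseline positives p = 20% or 80%; true mean change among positives −3.0 log10. Baseline negatives are assumed to stay negative, with a mean change of 0.

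Reported clearance = p(1 − f) + f, an excess of f(1 − p). Reported mean change = (1 − f) × true change.

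| f | p = 20% | p = 80% | Mean change |
|---|---|---|---|
| 5% | 0.19 + 0.05 = 24% | 0.76 + 0.05 = 81% | 0.95 × −3.0 = −2.85 |
| 10% | 0.18 + 0.10 = 28% | 0.72 + 0.10 = 82% | 0.90 × −3.0 = −2.70 |
| 20% | 0.16 + 0.20 = 36% | 0.64 + 0.20 = 84% | 0.80 × −3.0 = −2.40 |

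**5. Does the baseline covariate remove the dilution?** In a simulated single-visit regression on baseline (N = 50, 2,000 runs), the adjusted mean was 0.90 of the baseline-positive value at f = 10% and 0.80 at f = 20%. This is expected: with complete data, the adjusted mean at the average baseline equals the raw mean over all children.

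**6. Small groups.** Results are also summarized by age group (Protocol 2.10.4.1), and the planned minimum is 5 children in each of three groups. One baseline-negative child in 5 is f = 20%.

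**The case against.** The strongest reply is that little depends on this. Viral load is an exploratory objective. Clearance is in neither objectives table nor in the protocol's own pharmacodynamic list; only the SAP adds it. Efficacy is extrapolated in full from adults, the SAP plans no inferential comparisons, and exploratory analyses run only if the team finds them warranted. Summarizing every treated child is also a legitimate descriptive choice. All of this stands, and it limits the weight of the point. It does not justify a clearance date that rests on a pre-dose swab.

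A reader might also infer more than the documents support:
- *That baseline-negative children stay in every viral-load analysis.* The LLOQ rule for AUC may remove them there, and inclusion in the change from baseline is likely but not stated.
- *That their load is fixed at zero and cannot move.* The RP Ct normalization means that the analyzed value can shift either way.
- *That they are dated as cleared before dosing.* The swab precedes the dose, but the recorded date is Day 1, which is also the dosing date.
- *That the bias is known to be large.* Entry requires a recent positive sample and a symptom within 7 days, so f may be small. At f = 5% and p = 80%, the excess is 1 point.

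**Conclusion.** The point holds in limited form. As written, the clearance rule can give a wrong result for an individual child: cleared on Day 1, from a pre-dose swab, and carried forward. Baseline-negative children also raise the clearance proportion by f(1 − p) and, if their baseline counts as valid, shrink the mean fall by about the fraction f. Under the assumptions shown, the excess in clearance runs from 1 to 16 percentage points. That range is illustrative only, because f and p are not in the documents, and it assumes that baseline negatives stay negative. The effect on viral AUC cannot be determined from the text. The primary PK endpoint and the safety summaries are unaffected. The change is worth making because it corrects a rule and costs little, not because a study conclusion is at risk.

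**What to change.** Change the wording in SAP 6.10, 6.3.2, 6.11 and 6.16.1.1:
1. Count clearance, including the carry-forward in 6.3.2, from post-dose swabs only.
2. Make participants with a positive central Day 1 pre-dose swab the main set for clearance, time to clearance and change from baseline. Step 1 alone corrects the date, but a baseline-negative child with two post-dose negatives would still count as cleared.
3. Report the number negative on the central Day 1 swab, overall and by age group.
4. Keep the all-participant version as a sensitivity analysis.
5. State whether a below-LLOQ Day 1 value counts as missing for the AUC and, if not, what value it takes.
6. Say in SAP 6.1.4 and 6.3.3 whether a negative Day 1 swab is a valid baseline.

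The cost is SAP text only, with no new visit or sample. A few participants leave the main denominators for these summaries, which matters most in the smallest age groups. The sensitivity analysis keeps them visible.
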